4.3.1 Dose escalation rules

Dose escalation to a higher dose will be driven by an evaluation by the DSMB. At the time of DSMB evaluation, the last patient in the current dose level cohort must have received the 2nd dose and must have accumulated safety data for 8 weeks following the first dose. This allows for the DLT evaluation period to include an assessment of a potential delay in dose 2 due to toxicity concerns, as described for DLT number 5 in Section 4.3.2.

If one of the 3 patients in a dosing cohort experiences a DLT, 3 additional patients are added to the same dose level cohort. If 2 or more patients among these 6 patients experience DLTs, no further dose escalation can occur, and lower dose levels can be further explored. Dose escalation will continue until not more than 1 out of 6 patients experience DLT in a dose level cohort or the highest dose level group has completed treatment or no trial stopping criterion has been met. See Figure 2.

[figure not shown]

Figure 2: Dose-escalation according to a 3+3 design

Dose escalation will continue until not more than 1 out of 6 patients experiences a DLT in a dose level cohort (see DLT definitions in Section 4.3.2) or the dose level of

Clinical Study: ES2B-C001-S01 EU CT No.: 2024-516333-12-00

treatment has been completed (maximum administered dose MAD) or a trial stopping criterion has been met. The stopping criteria for dose escalation and trial are provided in Section 7.

Patients experiencing DLT will have their administration of adjuvanted or non-adjuvanted ES2B-C001 discontinued. These patients are allowed to remain in the trial to follow safety, disease progression and immune response. The DSMB will convene and recommend whether a re-start of these patients' treatment is advised and if a dose reduction may be required.

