4.3.2 Definition of Dose-limiting Toxicity (DLT)

A DLT is defined as any grade \geq 3 AE according to the NCI-CTCAE v. 5.0 observed at any time from the first administration of ES2B-C001 (alone or adjuvanted) to the 8 weeks thereafter, which despite standard supportive care and in the opinion of the Investigator, is possibly, probably, or definitely related to adjuvanted or non-adjuvanted ES2B-C001, or other event as described below. Investigators evaluation of relatedness to trial treatment administration should take concomitant medication into account.

DLTs will include:

- 1. Any grade ≥ 3 adverse events except:
 - a. Grade ≥ 3 nausea, vomiting, or diarrhea lasting ≤ 72hours with optimal medical therapy Grade 3 fatigue or anorexia lasting < 7 days.
 - b. Fever that occurs within 48 hours of IMP administration and resolves to Grade 2 within 48 hours and is fully resolved within 7 days.
 - c. Non-clinically relevant isolated biochemical abnormalities (e.g., isolated increase in gamma-glutamyltransferase [GGT]).
 - d. Laboratory values out of normal range without related clinical symptoms, clinically transient isolated in nature.
 - e. Laboratory abnormality that is asymptomatic and deemed by the Investigator not to be clinically significant.
- 2. Grade 3 autoimmune reactions, except Grade 3 autoimmune thyroiditis or other endocrine abnormality that can be managed by endocrine therapy.
- 3. Intolerable or > grade 3 injection-site reactions according to FDA guidance 2007 (table 16 appendix 2).
- 4. Grade 2 decrease in left ventricular ejection fraction (LVEF).
- 5. Treatment delay of >14 days due to any related adverse event(s).

In any case, the reported toxicity should be discussed between the Investigators and both the DSMB and the Sponsor. All toxicities will be graded using NCI-CTCAE Version 5.0 based on investigator assessment.

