8.3.6 Clinical Safety Laboratory Tests

Clinical laboratory tests will be performed by the laboratories mentioned in the study-specific Laboratory Manual. Samples will be collected in appropriate tubes and handled according to standard procedures of the applicable laboratory and according to the study-specific laboratory manual. Clinical laboratory variables will be determined as outlined in Table 13.

Table 13: Safety laboratory assessments

Clinical laboratory assessments				
Hematology	White blood cell (WBC) count Red blood cell (RBC) count Hemoglobin (Hb) Hematocrit (HCT) Mean corpuscular volume (MCV) Mean corpuscular hemoglobin (MCH) Platelet count	Lymphocytes (% and absolute) Neutrophils (% and absolute) Monocytes (% and absolute) Eosinophils (% and absolute) Basophils (% and absolute)		
Coagulation	Prothrombin time D-dimer Activated partial thromboplastin time			
Clinical chemistry	Alanine aminotransferase (ALT) Albumin Alkaline phosphatase (ALP) Aspartate aminotransferase (AST) Blood urea nitrogen (BUN) Calcium Creatinine Creatinine Kinase (CK) Troponin (T or I) Natriuretic peptides (NTproBNP)	Glucose Lactate dehydrogenase (LDH) Phosphorus Potassium Sodium Total bilirubin Uric acid C-reactive protein (CRP) Total protein		
Urinalysis	Bilirubin Blood Glucose Ketones Leukocytes Creatinine	pH Protein Specific weight Urobilinogen Nitrite Urine microscopic analysis (cells, bacteria, casts, crystals)		

Clinical Study: ES2B-C001-S01 EU CT No.: 2024-516333-12-00

- The investigator must review the laboratory results, document this review, and record any
 clinically significant changes occurring during the trial as an AE. The laboratory results must
 be retained with source documents.
- Abnormal laboratory findings associated with the underlying disease are not considered clinically significant unless judged by the investigator to be more severe than expected for the patient's condition.
- All laboratory tests with values considered clinically significantly abnormal during participation in the trial should be repeated until the values return to normal or baseline or are no longer considered clinically significant by the investigator or medical monitor.
 - If clinically significant values do not return to normal/baseline within a period of time judged reasonable by the investigator, the etiology should be identified, and the sponsor notified.

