9.3.1 Primary endpoint analysis

Total number and incidence of dose limiting toxicities (DLTs), number of patients with DTLs and percentage of patients with DLTs in each dose level and patient population will be reported.

Additionally, the number of DLTs, affected patients and percentage of affected patients will also be reported by preferred term and severity according to CTCAE v5.0 in each dose level and patient population.

The maximum tolerated dose will be determined for each patient population separately as lowest dose level at which ≥33% of patients have record of DLT.

The primary endpoint will be evaluated on the Safety Set.

Clinical Study: ES2B-C001-S01 EU CT No.: 2024-516333-12-00

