12.1 Definition of AE

AE Definition

- An AE is any untoward medical occurrence in a clinical trial patient, temporally associated with the use of trial intervention, whether or not considered related to the trial intervention.
- NOTE: An AE can therefore be any unfavorable and unintended sign (including an abnormal laboratory finding), symptom, or disease (new or exacerbated) temporally associated with the use of trial intervention.

Definition of Unsolicited AE

- An unsolicited AE is an AE that was not found using specific questions and that is communicated by a patient who has signed the informed consent. Unsolicited AEs include serious and nonserious AEs.
- Potential unsolicited AEs may be medically significant (i.e., symptoms or illnesses requiring
 a hospitalization, emergency room visit, or visit to/by a healthcare provider). The patients
 will be instructed to contact the site as soon as possible to report medically attended
 event(s), as well as any events that, though not medically attended, are of patient's
 concern. Detailed information about reported unsolicited AEs will be collected by qualified
 site personnel and documented in the patient's records.
- Unsolicited AEs that are not medically significant nor perceived as a concern by the patient will be collected during an interview with the patient and by review of available medical records at the next visit.

Events Meeting the AE Definition

- Any abnormal laboratory test results (hematology, clinical chemistry, or urinalysis) or other safety assessments (e.g., ECG, radiological scans, vital signs measurements), including those that worsen from baseline, considered clinically significant in the medical and scientific judgment of the investigator (i.e., not related to progression of underlying disease, or more severe than expected for the patient's condition).
- Exacerbation of a chronic or intermittent pre-existing condition including either an increase in frequency and/or severity of the condition.
- New condition detected or diagnosed after trial intervention administration even though it
 may have been present before the start of the trial.
- Signs, symptoms, or the clinical sequelae of a suspected drug-drug interaction.

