Grade 4	An AE that has life-threatening consequences; for which urgent intervention is indicated; that puts the subject at risk of death at the time of the event if immediate intervention is not undertaken; or that causes blindness or deafness.
Grade 5	The termination of life as a result of an AE.

Assessment of Causality

- The PI will assess the causality/relationship between the study drug and the AE based on medical judgment and considering the definitions of the "Assessment of Relationship of Adverse Events to Investigational Medicinal Product" described in Table 16, and all contributing factors. The investigator is obligated to assess the relationship between trial intervention and each occurrence of each AE/SAE.
- For causality assessment, the investigator will also consult the IB for ES2B-C001 and/or
 [adjuvant] . The investigator may change their opinion of causality in light of
 follow-up information and send an SAE follow-up report with the updated causality
 assessment.
- The causality assessment is one of the criteria used when determining regulatory reporting requirements.

Clinical Study: ES2B-C001-S01 EU CT No.: 2024-516333-12-00

Table 16: Assessment of relationship of Adverse Events (AEs) to investigational medicinal product (IMP).

	Assessment of Relationship of Adverse Events to IMP
Definitely Related	A clinical event, including laboratory test abnormality, occurs in a plausible time relationship to treatment administration, and which concurrent disease or other drugs or chemicals cannot explain. The response to withdrawal of the treatment (dechallenge*) should be clinically plausible. The event must be definitive pharmacologically or phenomenologically, using a satisfactory rechallenge† procedure if necessary.
Probably Related	A clinical event, including laboratory test abnormality, with a reasonable time sequence to administration of the treatment, unlikely to be attributed to concurrent disease or other drugs or chemicals, and which follows a clinically reasonable response on withdrawal (de-challenge). Rechallenge information is not required to fulfill this definition.
Possibly Related	A clinical event, including laboratory test abnormality, with a reasonable time sequence to administration of the treatment, but which could also be explained by concurrent disease or other drugs or chemicals. Information on treatment withdrawal may be lacking or unclear.

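### DLT exception 1d is garbled, with no significance test, time limit or grade cap, so the same laboratory event could be scored either way in the 3+3 count

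*Protocol*

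**What the plan says.** Protocol Section 4.3.2 defines a DLT as a Grade 3 or higher event by CTCAE v5.0, at least possibly related to treatment, within 8 weeks of the first dose. Item 1 then lists exceptions a to e. Three concern laboratory findings:

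- 1c exempts isolated biochemical abnormalities that are not clinically relevant.
- 1d exempts "Laboratory values out of normal range without related clinical symptoms, clinically transient isolated in nature".
- 1e exempts "Laboratory abnormality that is asymptomatic and deemed by the Investigator not to be clinically significant".

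The non-laboratory exceptions carry time limits. Under 1b, for example, fever is exempt if it starts within 48 hours of dosing and "resolves to Grade 2 within 48 hours and is fully resolved within 7 days".

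The count of patients with DLTs then drives decisions. Section 4.3.1 adds three patients after one DLT among three, and states: "If 2 or more patients among these 6 patients experience DLTs, no further dose escalation can occur". Section 9.3.1 ties the maximum tolerated dose (MTD) to a "dose level at which ≥33% of patients have record of DLT". The frequency of DLTs is also a primary endpoint (Section 3).

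**The concern.** A DLT exception has to give the same answer whoever applies it, because with three to six patients per level a single classification can change the next step. Item 1d does not do this. In its second clause the adverb *clinically* has nothing sensible to modify, so the reader must guess whether a word such as *insignificant* is missing. *Transient* is undefined, and nothing limits the exception to Grade 3.

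On one reading, a related Grade 3 or 4 laboratory event that is asymptomatic, isolated and eventually resolves is left out of the count. On another it is a DLT. The expand and stop steps, the MTD rule and the reported DLT frequency all inherit that ambiguity. So does the patient's own treatment, since Section 4.3.1 discontinues dosing after a DLT.

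**Working it through.** **Step 1. Set the exceptions side by side** (Protocol 4.3.2).

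| Item | Event | Time limit | Clinical-relevance test | Upper grade |
|---|---|---|---|---|
| 1a, first part | nausea, vomiting, diarrhoea | at most 72 hours | none | none |
| 1a, second part | fatigue, anorexia | under 7 days | none | Grade 3 |
| 1b | fever | Grade 2 within 48 hours, gone within 7 days | none | none |
| 1c | isolated biochemical abnormality | none | yes | none |
| 1d | out-of-range laboratory value | *transient*, undefined | none legible | none |
| 1e | asymptomatic laboratory abnormality | none | yes, by the investigator | none |

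Every item except 1d has either a stated duration or a clinical-relevance test. Item 1d has neither in usable form.

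**Step 2. Apply 1d to one event.** Take a related Grade 3 laboratory event, asymptomatic and isolated, that the investigator judges clinically significant and that resolves some time after 7 days.

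- As written, with *transient* meaning only that it resolved: exempt, not a DLT.
- As written, with *transient* borrowed from the limits in 1a and 1b: not exempt, a DLT.
- With *clinically insignificant* supplied: not exempt, a DLT. On this reading 1d largely repeats 1c and 1e.

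The text does not choose between these.

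**Step 3. Effect on the count** (rules from 4.3.1, cut-off from 9.3.1; no assumed rates).

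- First stage: 1/3 = 33.3% (add 3 patients) becomes 0/3 = 0% (no expansion). Change: 33.3 percentage points.
- Second stage: 2/6 = 33.3%, which is at or above 33% (no further escalation), becomes 1/6 = 16.7%, which is below it. Change: 33.3 − 16.7 = 16.6 points on rounded figures (exactly 1/6).

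**Step 4. Illustration under assumptions.** The protocol gives neither DLT rates nor a frequency for 1d events in the text available; the scenario results of Table 14 are not shown. Let p be the true DLT rate and f the share of DLT patients whose only qualifying event is exempted by 1d. The counted rate is q = p(1 − f), and for a standard 3+3 level

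P(pass) = (1 − q)³ + 3q(1 − q)² × (1 − q)³.

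With p = 0.33 (assumed):

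| f (assumed) | q | P(pass) |
|---|---|---|
| 0 | 0.33 | 0.434 |
| 10% | 0.297 | 0.500 |
| 25% | 0.2475 | 0.605 |
| 50% | 0.165 | 0.783 |

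These figures show direction only. Nothing in the protocol supports any particular f, including any f above zero, and the formula ignores DSMB judgement.

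The planned sample sizes reproduce (3 levels × 3 = 9; 3 levels × 9 = 27) and do not depend on 1d.

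**The case against.** The best defence is that this is a drafting slip with little consequence.

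*The stray adverb points to a lost clinical test.* This is plausible, and it is why the point is framed as ambiguity. But the text does not contain that test, and if it was intended, 1d is close to redundant and removing it costs almost nothing.

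*Few events qualify.* Table 15 describes Grade 4 as "An AE that has life-threatening consequences; for which urgent intervention is indicated", and puts events that are asymptomatic, or observations alone, in Grade 1. On that general text, an asymptomatic, transient laboratory event of Grade 3 or 4 is uncommon. This stands, and no rate is given.

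*The DSMB sees everything.* It assesses the adverse events of the DLT period, potential DLTs are escalated to it, Section 4.3.2 calls for discussion of reported toxicities, and it may recommend adding patients (Sections 4.3, 10.7). This limits the consequence. None of these provisions says how 1d is to be scored, however, and the adjudication task listed in 10.7 covers events already reported as DLTs.

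*The arithmetic is generic.* It is: any reclassified event in any 3+3 design has the same effect.

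Two stronger readings are tempting. First, laboratory changes become adverse events when they are "considered clinically significant in the medical and scientific judgment of the investigator" (Section 12.1), and Section 8.3.6 likewise records "clinically significant changes occurring during the trial as an AE". Since 1e already covers the insignificant ones, a reader might infer that what 1d adds must be clinically significant events. That does not follow. The same premise would leave 1c and 1e nothing to exempt, and those two already overlap, so the list was not written with each item doing separate work. Second, a reader might infer that 1d removes cardiac biomarker rises from the count. The protocol does not show that a rise meeting only the mild definition in Table 12 would be Grade 3 or higher, and below that grade item 1 does not reach it.

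**Conclusion.** The point holds as a defect in a decision rule. Item 1d does not parse and, as written, lacks a clinical-significance test, a duration and a grade cap. One available reading leaves a related, asymptomatic, isolated Grade 3 or 4 laboratory event out of the count used in 4.3.1 and 9.3.1.

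The possible effect is one step of the 3+3 rule per exempted event. The expected effect cannot be stated, because no event rate is given; it is zero if no such event occurs, and DSMB review reduces it further. The documents do not establish that the sponsor intended to exempt clinically significant events, or that cardiac biomarker signals are lost.

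The conclusion assumes that the published wording of 1d is complete. No redaction is marked there, but a word lost in the text cannot be fully excluded. If the approved copy contains *insignificant*, the significance gap closes, and what remains is the undefined *transient* and the overlap with 1c and 1e. The point should be corrected, but it does not undermine the design.

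**What to change.** Leave 1c and 1e as they are, and do one of the following.

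- **Delete 1d** and rely on 1c and 1e. This suits the sponsor if clinically insignificant was meant.
- **Reword 1d** as: *Grade 3 isolated laboratory abnormality with no associated symptoms, resolving to Grade ≤1 or baseline within 7 days.* The 7 days matches the longest limits in 1a and 1b; another stated limit would also serve.

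Under either option, a related, clinically significant Grade 4 laboratory event counts as a DLT. Rewording keeps a bounded exemption for short-lived Grade 3 findings; deletion makes their status depend on the relevance tests in 1c and 1e.

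The cost is a change to one sub-item, with no change to the planned 9 patients or the maximum of 27. Escalation becomes slightly more conservative, since an occasional laboratory event that 1d might have exempted may add three patients or stop escalation.

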2.4 Overall Benefit-Risk Conclusion

In conclusion, this trial aims to evaluate the safety profile of the novel HER2-directed vaccine ES2B-C001 with and without adjuvant. The risks for the patients participating in the trial are considered low and it is expected that the polyclonal anti HER2 antibody response will have anticancer effects beneficial to patients participating in the trial. The overall risk-benefit-ratio of participating in this trial is judged to be favorable in patients

3 Trial Objectives and Endpoints

Table 3: Description of the objectives and endpoints of this clinical study.

Objectives	Endpoints			
Primary				
To determine the safety, tolerability, maximum tolerated dose (MTD) for ES2B-C001 alone or in combination with the adjuvant	 Nature and frequency of dose-limiting toxicities (DLTs). Incidence, nature and severity of AEs graded according to the National Cancer Institute (NCI) Common Terminology Criteria for Adverse Events (CTCAE) v5.0. Incidence, nature and severity of injection site reactions according to FDA Guidance on Toxicity Grading Scales in Vaccine Trials (FDA, 2007). 			

Clinical Study: ES2B-C001-S01 EU CT No.: 2024-516333-12-00

Objectives	Endpoints			
Secondary				
To investigate the immunogenicity of ES2B-C001 alone or in combination with the adjuvant	 Immunogenicity as humoral immune response: Total anti-HER2 Immunoglobulin titers in sera by enzyme-linked immunosorbent assay (ELISA). Isotyping of anti-HER2 Immunoglobulins in sera (e.g. IgM, IgG (IgG1-4), IgD, IgE, IgA), Optional and obligatory in the non-adjuvanted and adjuvanted treatment group, respectively. 			
Exploratory				
To determine the preliminary antitumor activity of ES2B-C001 alone or in combination with the adjuvant observed	 Percentage of patients with measurable disease at baseline achieving Complete Remission (CR) or Partial Response (PR) according to RECIST 1.1 as assessed by the investigator during routine follow up. Percentage of patients with Disease Control Rate (DCR) according to RECIST 1.1 as assessed by the investigator during routine follow up. Progression free survival (PFS) in patients with Stable Disease (SD), or PR, at the time of first dosing of ES2B-C001 alone or in combination with the adjuvant according to RECIST 1.1. Disease-free survival (DFS) in patients with CR at the time of first dosing of ES2B-C001 alone or in combination with the adjuvant according to RECIST 1.1. Overall survival (OS) 			

4 Trial Design

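### Section 4.3.2 does not say how its DLT items interact: item 1 largely undoes item 2's endocrine exemption, the status of some Grade 3 injection-site reactions depends on the reading, and the grading sentence conflicts with item 3

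*Protocol*

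**What the plan says.** Section 4.3.2 of the protocol opens by defining a DLT as a CTCAE v5.0 Grade 3 or higher event within 8 weeks of the first dose that occurs despite standard supportive care and is at least possibly related, "or other event as described below". A numbered list follows.

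- **Item 1:** "Any grade ≥ 3 adverse events except", followed by exceptions a to e. These cover short gastrointestinal events, fatigue or anorexia, short fever, and isolated, asymptomatic or clinically irrelevant laboratory findings.
- **Item 2:** Grade 3 autoimmune reactions, "except Grade 3 autoimmune thyroiditis or other endocrine abnormality that can be managed by endocrine therapy".
- **Item 3:** "Intolerable or > grade 3 injection-site reactions according to FDA guidance 2007 (table 16 appendix 2").
- **Items 4 and 5:** a Grade 2 fall in LVEF, and a treatment delay of more than 14 days due to a related event.

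The section closes: "All toxicities will be graded using NCI-CTCAE Version 5.0 based on investigator assessment". Section 3, Table 3 makes one primary endpoint "Incidence, nature and severity of injection site reactions according to FDA Guidance on Toxicity Grading Scales in Vaccine Trials (FDA, 2007"), alongside CTCAE grading of adverse events. The FDA grading table in Appendix 2 is Table 17. Table 16 is the causality table.

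On consequences, Section 4.3.1 states "Patients experiencing DLT will have their administration of adjuvanted or non-adjuvanted ES2B-C001 discontinued" and "If one of the 3 patients in a dosing cohort experiences a DLT, 3 additional patients are added" to that dose level. Two or more DLTs among six patients stop escalation, and under Section 7.5 they temporarily halt enrolment. A DLT is also an event of special interest (Section 12.3), and the MTD is read from DLT frequencies (Section 9.3.1).

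**The concern.** The DLT definition drives every escalation decision, so an investigator should be able to classify an event from the text alone. Two kinds of event cannot be classified that way. One is a manageable Grade 3 endocrine event, which item 2 exempts and item 1 captures. The other is a Grade 3 injection-site reaction, which item 1 captures on the CTCAE scale and item 3 appears to place below its own threshold on the FDA scale. No sentence ranks the items, and the closing sentence names a different scale from the one in item 3.

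Local reactions matter for this product. Section 2.3 reports poor local tolerance of the adjuvanted vaccine in the toxicology study, and says that intolerable local reactions will lead to investigation of the non-adjuvanted vaccine, again without defining the term. With three patients per cohort, the classification of one event decides whether that patient's dosing is discontinued and whether the cohort doubles.

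**Working it through.** **Step 1. Apply the two possible readings to the two kinds of event.**

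| Related event | Union: meeting any item is a DLT | Specific item overrides item 1 |
|---|---|---|
| Grade 3 autoimmune thyroiditis, clinically significant, manageable | DLT under item 1 (no matching exception) | Not a DLT (item 2) |
| Injection-site reaction, CTCAE Grade 3, FDA Grade 3 or lower, not called intolerable | DLT under item 1 | Not a DLT (item 3, with > as printed) |
| Injection-site reaction, FDA Grade 4 | DLT (item 3) | DLT (item 3) |

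The union leaves item 2's exemption mostly idle. The override gives item 2 effect but drops some Grade 3 local reactions. In Table 17, FDA Grade 3 includes pain that needs a narcotic and swelling that prevents daily activity.

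**Step 2. A case in which the decision differs.** Two of three patients have a related injection-site reaction that is Grade 3 on both scales and not called intolerable. The union gives 2 DLTs and no escalation. The override gives 0 DLTs and escalation.

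**Step 3. An illustration of size.** The planned 9 patients (3 × 3) and the maximum of 27 (3 × 9) reproduce and do not depend on this point. The values of Table 14 are not visible, so there is no plan figure for operating characteristics to reproduce. The protocol gives no rate for the disputed local reactions, so the following inputs are assumptions:

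- q = per-patient probability of a disputed local reaction: 1%, 2% or 5%
- b = per-patient probability of any other DLT: 5%, independent of q
- two or more DLTs among the first three patients also reject the dose, as in a traditional 3+3 design (Figure 2 is not visible)

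Formulas:

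- p = 1 − (1 − q)(1 − b)
- P(reject the dose) = 1 − [(1 − p)³ + 3p(1 − p)⁵]
- P(expand from 3 to 6) = 3p(1 − p)²
- P(at least 1 of 9 patients classified differently) = 1 − [1 − q(1 − b)]⁹

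For q = 0.05: p = 1 − 0.95 × 0.95 = 0.0975, and P(reject) = 1 − (0.7351 + 0.1751) = 0.090.

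| q | p | P(reject) | P(expand) | P(≥1 of 9 differs) |
|---|---|---|---|---|
| 0 (events not counted) | 0.0500 | 0.027 | 0.135 | 0 |
| 0.01 | 0.0595 | 0.037 | 0.158 | 0.082 |
| 0.02 | 0.0690 | 0.048 | 0.179 | 0.159 |
| 0.05 | 0.0975 | 0.090 | 0.238 | 0.355 |

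Counting these events can only add DLTs, so the probability that the two readings give different decisions at one dose level is the difference in P(reject): about 0.010, 0.022 and 0.063.

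**Step 4. Sensitivity to b.** For q = 0, 0.01, 0.02 and 0.05, P(reject) is 0, 0.001, 0.005 and 0.027 with b = 0, and 0.094, 0.109, 0.125 and 0.176 with b = 0.10.

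**Step 5. Sensitivity to the printed sign.** If item 3 means ≥ Grade 3, a disputed event would have to be CTCAE Grade 3 but below FDA Grade 3. The differences in Step 3 then fall towards zero. The endocrine conflict and the closing sentence are unaffected.

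**The case against.** The strongest reply is that the section has a workable reading. The opening definition reaches beyond Grade 3 events, the list is introduced as what DLTs include, and items 4 and 5 plainly add events that item 1 would miss. Item 3 can be read in the same way: it adds reactions that are intolerable although below CTCAE Grade 3, and nothing in it says that only those reactions count. This stands. A reader might infer that the protocol excludes Grade 3 local reactions from the DLT count. The documents do not support that: it follows only if item 3 overrides item 1, which no text says.

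A reader might also infer that item 1 cancels the endocrine exemption outright. That is too strong. Exceptions c to e spare some asymptomatic or isolated laboratory findings, and a disorder controlled by endocrine therapy arguably does not persist despite standard supportive care. A clinically significant Grade 3 event is still left exposed to item 1, against item 2's evident purpose.

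On scales, CTCAE and FDA grading are parallel primary endpoints, and a sensible reader would use the FDA scale for item 3. The closing sentence nevertheless admits no exception.

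The > sign may be a ≥ lost in reading the PDF. The ≥ sign survives in item 1, but this cannot be settled from the text.

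Finally, the DSMB discusses each toxicity, weighs all safety data and may recommend restarting a patient, and its charter will hold further escalation instructions. That softens the consequences. It does not remove the ambiguity, because Section 10.7 has the DSMB judge reported DLTs against these same criteria.

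**Conclusion.** The point holds as a defect in how the DLT rule is written. On the union reading, which the wording favours, item 2's express exemption has little effect. On the override reading, a narrow group of Grade 3 local reactions goes uncounted, provided that > is as printed and *intolerable* is not invoked. On either reading, the closing sentence contradicts item 3 as to the grading scale.

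The size of the effect is unknown. The rejection probabilities of 3.7–9.0% (against 2.7%) and the 8–35% chance that at least one of 9 patients is classified differently are hypothetical. They rest on assumed rates that the protocol does not give. The adjuvant experience summarised in Section 2.3, mostly mild-to-moderate reactions, suggests that disputed events would be uncommon. A reader might infer a large effect by assuming that Grade 3 local reactions are frequent and all uncounted under item 3. The documents support neither assumption. The correction is worth making because DLT status governs dosing, cohort size, escalation and the MTD, and the cure is short.

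**What to change.** Make one edit to Section 4.3.2:

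1. State that injection-site reactions are assessed under both item 1 (CTCAE) and item 3 (FDA scale, Table 17) and that meeting either is a DLT. Confirm whether item 3 means > or ≥ Grade 3. A working definition of *intolerable* would also help, for example that the next dose is withheld or refused because of the reaction.
2. Add the endocrine events exempted in item 2 to item 1's exceptions.
3. Limit the closing sentence: toxicities are graded by CTCAE v5.0, except that item 3's criterion is graded on the FDA scale.
4. Correct the table reference in item 3 from 16 to 17 (clerical).

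The cost is a text change, mirrored in the DSMB charter, with no new data and no change in sample size. Step 1 does not loosen the rule for local reactions. Step 2 has a small downside: it loosens item 1 for manageable endocrine events relative to the literal union, although this is what item 2 already intends.
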